Grade 1	CT scans with lung windows. Repeat chest x-ray/CT scan every 12 weeks until return to baseline.	No therapy required	Administer 100% of everolimus dose.
Grade 2	CT scan with lung windows. Repeat CT scan at least every 12 weeks until return to within normal limits. Consider bronchoscopy with biopsy and /or BAL.	Symptomatic only. Consider corticosteroids if cough is troublesome.	Consider interruption of everolimus until recovery to \leq Grade 1. Study. Restart treatment at a reduced dose. Patients will discontinue everolimus if they fail to recover to $<$ Grade 1 within 4 weeks
Grade 3	CT scan with lung windows. Repeat at least every 8 weeks until return to within normal limits. Bronchoscopy with biopsy and/or BAL is recommended.	Prescribe corticosteroids if infective origin ruled out. Taper as medically indicated.	Hold everolimus treatment until recovery to \leq Grade 1. May restart treatment within 4 weeks at a reduced dose (by one level**) if evidence of clinical benefit.
Grade 4	CT scan with lung windows and required pulmonary function testing including spirometry, DL _{CO} , and room air O ₂ saturation at rest. Repeat at least every 8 weeks until return to within normal limits. Bronchoscopy with biopsy and/or BAL is recommended if possible.	Prescribe corticosteroids if infective origin ruled out. Taper as medically indicated.	Discontinue everolimus treatment.

Table 17: Management of non-infectious pneumonitis

Both asymptomatic radiological changes (Grade 1) and symptomatic non-infectious pneumonitis (Grade 2 = not interfering with activities of daily living and Grade 3 = interfering with activities of daily living and oxygen indicated) have been noted in patients receiving everolimus therapy. Non-infectious pneumonitis has been associated with everolimus and other mTOR inhibitors (Atkins et al. 2004). If non-infectious pneumonitis develops, a consultation with a pulmonologist should be considered. If the patient develops Grade 3 pneumonitis, treatment with everolimus must be interrupted and the patient treated as medically indicated (short course corticosteroids, oxygen, etc.). Management of non-infectious pneumonitis suspected to be associated with everolimus (TABLE 17) and dose modification instructions are provided in TABLE 14 , TABLE 15 and TABLE 16.

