8.5.4 Prohibited concomitant therapy

Use of the following treatments is NOT allowed during the study:

- Investigational or commercial anticancer agents, such as chemotherapy, immunotherapy, targeted therapy, biological response modifiers, or endocrine therapy other than the once listed must not be given to patients.
- Hormone replacement therapy, topical estrogens (including any intra-vaginal preparations), Megestrol acetate and selective estrogen-receptor modulators (e.g. Raloxifene) are prohibited.
- Patients receiving concomitant immunosuppressive agents or chronic corticosteroids use, after taking the first dose of study drug in cases outlined below: Topical applications (e.g. rash), inhaled sprays (e.g. obstructive airways diseases), eye drops or local injections (e.g. intra-articular) are allowed. Long term low dose therapy, i.e. ≤ 10 mg/d prednisolone equivalent is permissible.
- Hematopoietic growth factors (e.g. Erythropoietins, G-CSF and GM-CSF) are not to be administered prophylactically. Use of these must be reserved to cases of Grade 3 or 4 neutropenia and anemia as per the labeling of these agents.
- Where possible, it is recommended to avoid drugs or substances known to be inhibitors or inducers of the isoenzyme CYP3A:
 - Co-administration with strong CYP3A inhibitors (e.g. Ketoconazole, Itraconazole, Ritonavir), and strong inducers (e.g. Rifampin, Rifabutin) should be avoided.
 - Co-administration with moderate CYP3A inhibitors (e.g. erythromycin, fluconazole, calcium channel blockers, benzodiazepines) and moderate inducers (e.g., carbamazepine, phenobarbital, phenytoin) should also be avoided if possible or otherwise subject to caution (e.g. increased frequency of safety monitoring).
 - Inhibitors – prohibited 7 days before dosing (6 months for amiodarone) and during protocol treatment
 - Inducers – prohibited 14 days before dosing and during protocol treatment

Sevilla orange, grapefruit and grapefruit juice affect cytochrome P450 and P-gp activity and must therefore be avoided during study drug intake.

Because the composition, pharmacokinetics and metabolism of many herbal supplements are unknown, concurrent use of all herbal supplements is prohibited during protocol treatment.

APPENDIX VI – PROHIBITED MEDICATIONS lists clinically relevant CYP3A inhibitors, inducers and the definition of strong and moderate inhibitors/inducers.

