Die Therapie mit Everolimus wird den Patientinnen zusammen mit der indizierten endokrinen Therapie verabreicht. Die Einnahme erfolgt einmal täglich möglichst zur gleichen Tageszeit. Die Behandlung mit Everolimus sollte - wenn medizinisch indiziert – über die randomisierte Phase hinaus verlängert werden. Die Everolimus-Dosierung erfolgt in Abhängigkeit von der vorgesehenen endokrinen Therapie. Es dürfen nur die in der Tabelle aufgeführten Behandlungspläne verwendet werden.

Endokrine Therapie		+Everolimus
Exemestan (Baselga et al. 2012 – BOLERO 2-trial) Vorangegangene Therapie mit Letrozol/ Anastrozol	25 mg/d	10 mg/d*
Tamoxifen (Bachelot et al. 2011 – TAMRAD-trial) Vorangegangene Therapie mit AI	20 mg/d	10mg/d*
Letrozol (Baselga et al. 2009 [neo-adjuvant, Phase II]; Awada et al. 2008 [MBC, Phase I])	2,5 mg/d	10mg/d*
Anastrozol	1 mg/d	10mg/d*

* Everolimus wird entsprechend der Zulassung verschrieben. Der behandelnde Prüfarzt entscheidet über eine Dosisanpassung, die der individuellen medizinischen Notwendigkeit der Patientin entspricht. Eine Start-Dosis von 5mg pro Tag ist erlaubt, sofern diese medizinisch indiziert ist. Die Entscheidung über die Behandlung der Patientin mit Everolimus wird unabhängig von der Studie getroffen.

Tabelle 29: Empfohlene Dosierung der endokrinen Therapie in Kombination mit Everolimus

Nach Beginn der Behandlung mit Everolimus wird die Dosierung je nach Dosierung der verabreichten Standard-Therapie und in Abhängigkeit der aufgetretenen Nebenwirkungen angepasst. Die tägliche Maximaldosis von Everolimus beträgt 10 mg, die Minimaldosis ist 5 mg alle zwei Tage. Die Gabe von Everolimus erfolgt über 12 Monate und kann nach der Behandlungsphase bei entsprechender medizinischer Indikation verlängert werden. Everolimus wird außerhalb der Zulassung mit Exemestan unter Studienbedingungen von Novartis für die Dauer der individuellen Studienteilnahme (inklusive 2 Jahre Follow-Up-Phase) zur Verfügung gestellt. Ein vorzeitiger Abbruch der Therapie erfolgt bei Progress der Erkrankung oder aus anderen Gründen für einen vorzeitigen Therapieabbruch. Eine Beendigung oder Modifikation der Therapie ist entsprechend der Einschätzung des behandelnden Arztes auch aus anderen Gründen möglich.

Therapie mit Ribociclib in Kombination mit einer endokrinen Standardtherapie (DIVa):

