Ketoconazole	AUC ↑ 15.3-fold (Range 11.2-22.5) C _{max} ↑ 4.1-fold (Range 2.6-7.0)	Concomitant treatment of everolimus and potent inhibitors is not recommended.
Itraconazole, posaconazole, voriconazole	Not studied. Large increase in everolimus concentration is expected.	
Telithromycin, clarithromycin		
Nefazodone		
Ritonavir, atazanavir, saquinavir, darunavir, indinavir, nelfinavir		
Moderate CYP3A4/PgP inhibitors		
Erythromycin	AUC ↑ 4.4-fold (Range 2.0-12.6) C _{max} ↑ 2.0-fold (Range 0.9-3.5)	Use caution when co-administration of moderate CYP3A4 inhibitors or PgP inhibitors cannot be avoided. If patients require co-administration of a moderate CYP3A4 or PgP inhibitor, dose reduction to 5 mg daily or 5 mg every other day may be considered. However, there are no clinical data with this dose adjustment. Due to between subject variability the recommended dose adjustments may not be optimal in all individuals, therefore close monitoring of side effects is recommended.
Verapamil	AUC ↑ 3.5-fold (Range 2.2-6.3) C _{max} ↑ 2.3-fold (Range 1.3-3.8)	
Ciclosporin oral	AUC ↑ 2.7-fold (Range 1.5-4.7) C _{max} ↑ 1.8-fold (Range 1.3-2.6)	
Fluconazole	Not studied. Increased exposure expected.	
Diltiazem		
Amprenavir, fosamprenavir	Not studied. Increased exposure expected.	
Grapefruit juice or other food affecting CYP3A4/PgP	Not studied. Increased exposure expected (the effect varies widely).	Combination should be avoided.
Potent CYP3A4 inducers		
Rifampicin	AUC ↓ 63% (range 0-80%) C _{max} ↓ 58% (range 10-70%)	Avoid the use of concomitant potent CYP3A4 inducers. If patients require co-administration of a potent CYP3A4 inducer, an everolimus dose increase from 10 mg daily up to 20 mg daily should be considered using 5 mg increments applied on Day 4 and 8 following start of the inducer. This dose of everolimus is predicted to adjust the AUC to the range observed without inducers. However, there are no clinical data with this dose adjustment. If treatment with the inducer is discontinued, the everolimus dose should be returned to the dose used prior to initiation of the co-administration.
Corticosteroids (e.g. dexamethasone, prednisone, prednisolone)	Not studied. Decreased exposure expected.	
Carbamazepine, phenobarbital, phenytoin	Not studied. Decreased exposure expected.	
Efavirenz, nevirapine	Not studied. Decreased exposure expected.	

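### Appendix VI opens a path to everolimus 20 mg daily with a potent CYP3A4 inducer, while Section 8.5.4 prohibits inducers during treatment and the German synopsis states a 10 mg daily maximum

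*Protocol*

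**What the plan says.** **Inducers.** Section 8.5.4 opens its list with "Use of the following treatments is NOT allowed during the study". Its CYP3A bullet first recommends avoiding inhibitors and inducers as far as possible, then says strong inducers should be avoided and moderate ones avoided if possible or used with caution. It ends with "Inducers – prohibited 14 days before dosing and during protocol treatment". The first table of Appendix VI, which is titled as a list of prohibited medications, gives rifamycins, phenytoin, carbamazepine, barbiturates, efavirenz and nevirapine a 14-day wash-out. The second table of the same appendix reads "Avoid the use of concomitant potent CYP3A4 inducers. If patients require co-administration of a potent CYP3A4 inducer", and continues that "an everolimus dose increase from 10 mg daily up to 20 mg daily should be considered", in 5 mg steps on two dates. It adds that no clinical data exist for this adjustment.

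**Everolimus dose.** The German synopsis (Appendix I) states "Die tägliche Maximaldosis von Everolimus beträgt 10 mg" and restricts treatment to the tabulated regimens, all at 10 mg daily (a 5 mg start is allowed). In English, Table 13 gives 10 mg daily, and its footnote refers to the approved label and to the physician's judgement on dose changes. Section 8.2.2.1 describes one upward step, from 5 to 10 mg, and Table 14 contains reductions only. No maximum is stated in English.

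**Corticosteroids.** The second table of Appendix VI lists "Corticosteroids (e.g. dexamethasone, prednisone, prednisolone") among potent inducers, with no limit on dose or duration. The first table restricts chronic oral use above stated doses and allows short courses of up to 2 weeks. Section 8.5.4 allows long-term treatment at up to 10 mg/d prednisolone equivalent. For grade 3 pneumonitis Table 17 says "Prescribe corticosteroids if infective origin ruled out", followed by a taper, and permits a restart of everolimus at a reduced dose. Section 8.2.2 says a dose reduced for adverse events should not be raised again.

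**The concern.** The condition that triggers the dose increase in Appendix VI, a required potent inducer during treatment, is the situation that Section 8.5.4 rules out. One appendix both prohibits a set of drugs and gives a dosing path for continuing with them. The path leads above the only everolimus maximum that the protocol states.

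This concerns the dose of an investigational drug. Sites that read different pages could handle the same patient differently: refuse the inducer, stop everolimus, keep the dose, or raise it. Each could cite the protocol in support.

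**Working it through.** The protocol gives no figure for this point, so the check is mainly a comparison of texts.

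1. **Is an inducer permitted during treatment?**
   - Section 8.5.4, lead-in and last line on inducers: no.
   - Section 8.5.4, preceding lines of the same bullet: avoid, with caution for moderate inducers where they cannot be avoided.
   - Appendix VI, first table: prohibited, 14-day wash-out.
   - Appendix VI, second table: avoid, but if required, consider a higher everolimus dose.
   - Result: the first and last cannot both apply to the same patient.

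2. **How high may everolimus go?**
   - Appendix VI: 10 mg + 5 mg + 5 mg = 20 mg daily.
   - German synopsis: 10 mg daily.
   - Ratio: 20 / 10 = 2.
   - English treatment section: no stated maximum, and no upward step beyond 10 mg.

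3. **Are the inducers classified consistently?** Section 8.5.4 names carbamazepine, phenobarbital and phenytoin as moderate and refers to Appendix VI for the definitions. Appendix VI lists the same three under potent inducers. A site applying 8.5.4 would therefore not see these drugs as meeting the Appendix VI condition; a site applying Appendix VI would.

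4. **Do corticosteroids for pneumonitis create opposite dose instructions?** For grade 3, Table 17 holds everolimus until recovery to grade 1 or less. Table 15 stops it and suggests steroids until recovery to that grade, then a possible restart at a lower dose. In that sequence everolimus is off while the steroid is given, so there is no co-administration and the increase advice does not apply. If the taper in Table 17 runs past the restart, the patient is on a reduced dose that Section 8.2.2 says should not be raised, while also taking a drug for which Appendix VI says an increase should be considered. The first Appendix VI table allows up to 2 weeks of steroids but does not say whether the increase advice then applies.

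5. **How many patients?** Section 15.3 plans 90 everolimus patients. In the phase III data of Table 7 (everolimus plus exemestane), pneumonitis occurred in 12% at any grade, 3% at grade 3 and 0% at grade 4.
   - Grade 3: 0.03 × 90 = 2.7, about 3 patients.
   - Only those whose taper outlasts the restart meet the conflict in step 4, and the protocol gives no rate for that.
   - It also gives no rate for needing any other inducer during treatment.

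**The case against.** The strongest defence is that Appendix VI is conditional: it first says to avoid potent inducers and only asks that an increase be considered. Section 8.5.4 is itself mixed, and most of its bullet agrees with Appendix VI. The 10 mg maximum stands only in the German synopsis, in a paragraph about adjustment for standard therapy and side effects, while the English text defers to the label and to the physician. All of this is accurate. It does not remove the conflict, because the explicit prohibition during treatment is current text and the discretion in the Table 13 footnote does not cancel the synopsis maximum.

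Some stronger readings are tempting but not supported:

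- **That every patient given steroids for pneumonitis receives opposite dose instructions, about 11 of 90.** The figure is 0.12 × 90 = 10.8 and uses the any-grade rate. Table 17 requires no therapy at grade 1 and only suggests considering steroids at grade 2. At grade 3 everolimus is held first, and Section 8.2.3.1 speaks of a short course.
- **That all 90 everolimus patients are exposed.** That is the cohort size; an inducer wash-out is required before inclusion.
- **That the efficacy analysis is compromised.** Under Section 15.2 the primary analysis uses the ITT set and the PP set is only supportive, so uncertainty over who was treated according to protocol is a minor matter here.
- **That only one absolute maximum would be coherent.** A general limit with a stated exception would also be consistent.

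**Conclusion.** The contradiction is real and stands in the current text. Section 8.5.4 and the first Appendix VI table prohibit inducers, while the second Appendix VI table gives a dosing path with them to 20 mg daily, twice the maximum in the German synopsis. The moderate versus potent labelling of three anticonvulsants is a further plain inconsistency. The corticosteroid overlap is narrower: it depends on a taper continuing after everolimus restarts.

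The number of patients affected cannot be estimated from the protocol. If the grade 3 pneumonitis rate in Table 7 carries over to this cohort, about 3 of 90 patients would reach the situation in which the steroid conflict could arise, and fewer would meet it. The point rests on patient safety and consistent conduct across sites rather than on the statistics. It should be settled because it concerns the dose of an investigational drug. Nothing here says which dose or rule is correct.

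**What to change.** The sponsor should reconcile Section 8.2.2 (no increase after a reduction), Table 17, Section 8.5.4, the German synopsis in Appendix I and both tables of Appendix VI, so that:

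- the rule on CYP3A4 inducers during treatment is the same everywhere;
- each named inducer carries one classification;
- the everolimus dose limit agrees between the German synopsis, the English treatment section and Appendix VI;
- the position of corticosteroids is explicit, including a taper that continues after everolimus restarts;
- any exception is written out where the rule stands.

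The content of each rule is for the sponsor's clinical team. The cost is wording in a protocol amendment; sample size, assessments and analysis are unaffected.

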APPENDIX VII – NEW YORK HEART ASSOCIATION CLASSIFICATION OF CARDIAC DISEASE

Clinical Evaluation of Functional Capacity of Patients with Heart Disease in Relation to Ordinary Physical Activity				
Class	Cardiac Symptoms	Limitations	Need for Additional Rest *	Physical Ability to Work **
I	None	None	None	Full time
II	Only moderate	Slight	Usually only slight or occasional	Usually full time
III	Defined, with less than ordinary activity	Marked	Usually moderate	Usually part time
IV	May be present even at rest, and any activity increases discomfort	Extreme	Marked	Unable to work

* To control or relieve symptoms, as determined by the patient, rather than as advised by the physician.
 ** At accustomed occupation or usual tasks.
 Reference: Bruce, RA: Mod Concepts Cardiovasc Dis 25:321, 1956. (Modified from New York Heart Association, 1953)

